3. STUDY DESIGN

Forty PMDD subjects will be recruited. Menstrual cycle phase will be established by measuring the mid-cycle LH surge using a urinary colorimetric assay (Clearblue® colorimetric LH assay, Princeton, New Jersey). Failure to ovulate will exclude the subject from participating that month, and the study will be postponed until a following month when ovulation can be documented.

Overall Design (see Figure 1): Month 1 consists of a screening evaluation using daily mood ratings (DMR) (see Section 6: Subject Selection). In Month 2, evaluations are continued, the Structured Clinical Interview for DSM-IV (SCID)^{51, 52} and documentation of ovulation by the LH surge (approximately menstrual cycle day 14) are performed. In the Month 2 luteal phase, PMDD subjects will collect overnight urine samples for 6-SMT and reproductive hormones (RH) (estradiol, progesterone, FSH, LH, prolactin) starting 8-9 days after the LH surge (approximately menstrual cycle days 22-23). These baseline urine sample collections are timed to coincide with post-intervention measures in months 3 and 5. Starting in Month 3, after the LH surge (luteal phase), subjects will undergo a night of LWT (sleep 21:00-01:00 h, followed by wake) vs. EWT (wake until 03:00 h followed by sleep until 07:00 h) at home. We selected the specific wake and sleep times based on our previous work in

PMDD.^{36, 37} The following day, subjects will receive the light intervention for 7 consecutive days: days 1-7 after the LH surge (approximately menstrual cycle days 15-21). We will randomize subjects to 60 min of either AM bright white light (LED of 1350 lux at 20 inches) starting within 30 minutes of their habitual wake time, or PM bright white light ending 30 min before their habitual sleep onset time. After completing seven days of light exposure, subjects again will collect 30+ hours of urine samples over 2 nights (between days 8-9 after the LH surge, approximately menstrual cycle day 22-23). The following Month 4 (Washout) will be a month of no intervention to prevent any carry-over effects from the Month 3 intervention affecting measures in Month 5. Mirroring Month 3 timing, in the luteal phase of Month 5, subjects will receive the alternate wake therapy (LWT or EWT) and light exposure (AM or PM), followed by 2 overnight collections of urinary 6-SMT and RH samples. See Fig. 1, below.

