This design allows us to complete the studies at least two days before the next expected menstrual period. Measuring the circadian profile of urinary melatonin over 2 nights for 30+ h will allow us to assess phase, duration and amplitude changes of melatonin reflective of the underlying circadian pacemaker. In addition, we will assess phase-shift responses of melatonin to light in relation to other critical biological rhythm measures of sleep and activity. To document the sleep/wake cycle and exposure to light intensity and spectra, we will use the Actiwatch device (see description below).

[figure not shown]

Figure 1. Study flow: The luteinizing hormone surge (LHS) documents ovulation, c. menstrual cycle day (CD) 14. Urine samples for 6-sulphatoxy-melatonin (6-SMT) and reproductive hormones (RHs) will be collected for 30+ hours over 2 nights between days 8-9 after the LH surge (c. CD 22-23) in months 2,3,5; actigraphy will begin the day of LHS and continue until day 10 after the LHS (CD 14-24) of months 2,3,5; late wake therapy (LWT) or early wake therapy (EWT) will be administered at home on the night of the LHS; bright morning (AM) or evening (PM) light will be administered on days 1-7 after the LHS (CD 15-21) in a counterbalanced, cross-over design in months 3 and 5. Mood ratings (HRSD+BDI) will be collected as follows: Months 1 & 2 – once per week; Months 3 & 5 – LHS + 0 (Pre-

LWT/EWT), daily LHS +1 → LHS + 2 and once the evening after last treatment (LHS +7/8). Visual Analogue Scales (VAS) for depressed mood, anxiety, affective lability, irritability (Daily Mood Ratings)(core PMDD symptoms) collected daily during Months 1 & 2, and twice daily on LHS + 0 through LHS + 2 (for wake therapy effects) and daily LHS + 3 through LH + 10 (for light treatment effects) in Months 3 & 5. HRSD will be collected once during Month 4 and a once a month after Intervention 2 to monitor relapse.

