During an initial 2-3 month evaluation period, subjects will complete twice-daily self ratings of mood (including core PMDD symptoms of depression, anxiety, affective lability, irritability) using a 100 mm visual analogue scale (Daily Mood Ratings form-DMR).^{54, 55} Individual items on the DMRs will be measured, scored and plotted using GraphPad Prism (GraphPad Software, Inc. La Jolla, CA) to observe the daily progression of mood symptoms (both in the morning and evening from day to day in the follicular and luteal phase) throughout the evaluation phase and in relation to the woman's menses to ensure proper diagnosis based on DSM-IV criteria. Women also will visit the clinic on a weekly basis where the project coordinator will collect the daily rating forms, and a trained clinician, blind to treatment condition, will interview the subjects using the 24-item Hamilton Rating Scale for Depression (HRSD).⁵⁶ At this time the subjects also will complete a Beck Depression and Anxiety Inventory.^{57, 58} In addition, we will ask them to complete a screening questionnaire on their sleep patterns, to keep daily sleep logs and to adhere to their habitual sleep schedule. This evaluation period will establish the diagnosis of PMDD and will provide information as to when symptoms are likely to occur. It also helps us to design a study schedule based on each patient's individual symptom patterns, and to establish each individual's sleep schedule prior to interventions. As in our previous studies and those of others,⁵⁹ we expect about 5% of patients screened to meet criteria. We especially will recruit women who are non-responsive to other interventions for PMDD, or who seek alternatives to pharmacological or chronic treatments for PMDD.

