5. STUDY INTERVENTIONS

5.1 Interventions, Administration, and Duration

Treatment 1 will occur during the menstrual cycle immediately following the 2 menstrual cycles studied in the evaluation period. Washout will occur the following menstrual cycle, and Treatment 2 the menstrual cycle immediately following Washout. As we establish the Evaluation Period as Month 1 and Month 2, we will refer to Treatment 1 as occurring in Month 3, Washout in Month 4, and Treatment 2 in Month 5 (see section 6.1).

During Month 3, qualified participants will sign the Study Consent between cycle days 1 and 10, be randomized to treatment and receive all necessary instructions, forms and equipment to continue with the treatment phase. On the day of their luteinizing hormone (LH) surge (luteal phase), subjects will undergo a night of Late Wake Therapy (LWT) (sleep 21:00-01:00 h, followed by wake) vs. Early Wake Therapy (EWT) (wake until 03:00 h followed by sleep until 07:00 h) at home. We selected the specific wake and sleep times based on our previous work in PMDD.^{36, 37} The following day, subjects will receive the light intervention for 7 consecutive days: days 1-7 after the LH surge (approximately menstrual cycle days 15-21). Depending on their randomization schedule, subjects will receive, at home, 60 min of either AM bright white light (LED of 1350 lux at 20 inches) starting within 30 minutes of their habitual wake time (for those undergoing LWT), or PM bright white light ending 30 min before their habitual sleep onset time (for those undergoing EWT). The following Month 4 (Washout) will be a month of no intervention to prevent any carry-over effects from the Month 3 intervention affecting measures in Month 5. Mirroring Month 3 timing, in the luteal phase of Month 5, subjects will receive the alternate wake therapy (LWT or EWT) and light exposure (AM or PM) (see Fig. 1, above).

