6.2.3 Blinding

The principal investigator and clinical rater will remain blind to treatment condition until completion or discontinuation of participant from study. As patients will be coded, one statistician and technician and supervisor running assays also will be blind to patient name and treatment condition. Members of the Data Safety Monitoring Committee will review records in which patient names are coded, unless the code needs to be broken in the event of an adverse outcome. All other lab personnel will not be blind to treatment as the study coordinator and research associate prepare patient equipment and instruct patients on proper completion of the treatment protocol, the data manager and quality assurance officer enter all data into the database (including treatment condition). Due to the nature of the treatment (sleep, light intervention), patients will not be blind to condition.

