6.2.4 Treatment Visits

In accordance with the Schedule of Evaluations (section 6.1 above), treatment-related measures will be collected in months 3 and 5 as follows:

- Hamilton: The Hamilton Rating Scale for Depression (HRSD)⁵⁶ (as a validated objective, interview-based assessment of depression). Atypical depression symptoms as part of the Structured Interview Guide for the Hamilton Depression Rating Scale, Seasonal Affective Disorders version (SIGH-SAD)⁶⁰ (as atypical symptoms in particular respond to light treatment⁶¹) Mania⁶² ratings (to document any clinical induction of manic symptoms by the wake or light interventions) – on ovulation night (LSH), daily on LHS+1 – LHS+2 (during intervention) and once after light treatment on LHS+8-9 (post-intervention assessment).
- Beck Depression Inventory (BDI)⁵⁷ (as a validated subjective assessment of depression) – on ovulation night (LSH), daily on LHS+1 – LHS+2 (during intervention) and once after light treatment on LHS+8-9 (post-intervention assessment),
- Beck Anxiety Inventory (BAI)⁵⁸ (as many women with PMDD report anxiety symptoms)⁶³ – on ovulation night (LSH), daily on LHS+1 – LHS+2 (during intervention) and once after light treatment on LHS+8-9 (post-intervention assessment),
- The Psychological General Well-Being Index (PGWI)⁶⁴ – on ovulation night (LSH), daily on LHS+1 – LHS+2 (during intervention) and once after light treatment on LHS+8-9 (post-intervention assessment),

- Daily mood self-ratings (DMR)⁵⁴ that include core PMDD symptoms of anxiety and irritability – collected daily on LHS+0 through LHS+2 (for wake therapy effects) and daily LHS+3 through LHS+10 (for light treatment effects),
- Pittsburgh Sleep Quality Index (PSQI)⁶⁷ to assess subjective sleep quality – once on LHS+8-9 (post-intervention assessment),
- Visual analogue scale⁶⁸ to assess subjective sleep quality – once on LHS+8-9 (post-intervention assessment),
- Ovulation testing performed for 7 days starting on menstrual cycle day 10 in months 3 and 5 to determine luteinizing hormone surge (LHS). Participants will contact Study Coordinator with their time of first menses (cycle day 1) to determine cycle day 10 and schedule appointment for collecting study forms and equipment,
- Actigraphy will be collected for 10 days starting the day of LHS to monitor baseline sleep, light and activity measures at home,
- Urine collection for 30 hrs performed between days 8-9 after LHS.

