Specifically, data for hypothesis 1.A. will be analyzed using a Random Regression Model (RRM), a generalized linear model described by Gibbons et al.,⁷⁴ Hedeker et al.⁶⁹ and Laird.⁷⁵ The random effects method has several advantages over more traditional analytic approaches such as a change score, end-point or repeated measures analysis of variance. This method allows the inclusion of subjects with missing data or those who were terminated early in the study, without relying on data imputation procedures. This method provides an estimate of the individual variability around the population trend, the variability of the individual intercepts (baseline values) and slopes (changes across time), and the correlation between them. A fully saturated treatment by time model will be utilized for inference. Co-variance structure will be chosen based on Akaike's Information Criterion (AIC). Random treatment effects also will be evaluated for importance based on the model AIC. This plan allows for any group level effects to be incorporated into the model. Denominator degrees of freedom will be calculated using the Kenward-Roger small sample correction. All subjects will be included in the analyses, and we will not focus only on subjects who complete the study. Our methods for data analyses include all subjects with any valid data points in the analyses. Secondary analyses will be performed on data from completers. Type 1 error will be controlled by correcting the p-value per domain. For hypothesis 1.B, an individual's slope for each of the dependent variables listed above will be calculated and will be used for correlational analysis using the Pearson method. In addition, we will examine the number of responders. The operational definition of the criteria for

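### The blind rater's Hamilton call on LHS+1 follows a wake night whose timing differs by arm, so it is likely to disclose the arm; the plan has no safeguard and does not say how that day's scores are used

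*Combined protocol and SAP*

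**What the plan says.** **Wake night.** The Figure 1 text in Section 3 states that "late wake therapy (LWT) or early wake therapy (EWT) will be administered at home on the night of the LHS". Section 3 gives the two schedules as "a night of LWT (sleep 21:00-01:00 h, followed by wake) vs. EWT (wake until 03:00 h followed by sleep until 07:00 h", and Section 5.1 repeats them.

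**Rating days.** Section 6.2.4 places the HRSD and BDI on the day of the surge, then "daily on LHS+1 – LHS+2 (during intervention) and once after light treatment on LHS+8-9 (post-intervention assessment". The Figure 1 text has the same early days but a different last rating: "daily LHS +1 → LHS + 2 and once the evening after last treatment (LHS +7/8".

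**Instrument and mode.** Under Section 4.3 a clinician "will interview the subjects using the 24-item Hamilton Rating Scale for Depression (HRSD". The items are not printed. Section 6.2.4 has the HRSD during and after the intervention done by telephone. A footnote to the schedule in 6.1 says the Hamilton and Beck evaluations on the starred early days are by phone.

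**Blinding.** Section 6.2.3: "The principal investigator and clinical rater will remain blind to treatment condition until completion or discontinuation of participant from study". The same section says that patients cannot be blinded. On the BDI, Section 6.2 has the research associate collect and score it and pass it to the rater for review, while Section 10.1 has the blind rater collect all mood forms.

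**Analysis.** Section 9.5.1 defines the mood outcome as change from Month 2 to post-intervention, but its description also covers ratings made during treatment. Section 9.6 says "A fully saturated treatment by time model will be utilized for inference" and does not list the time points.

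**The concern.** Patients know their assignment, so the rater's blind is the only masking that protects the HRSD. The LHS+1 call puts an interviewer who must not know the arm in conversation with someone who has just been kept awake either early or late in the night. Any question about when she slept elicits the feature that separates the arms. Nothing in the plan removes such questions, asks women to withhold their sleep times, uses a different rater for these calls, or tests whether the blind held.

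A second, smaller issue is scoring. If sleep items are rated as usual on LHS+1, they record the assigned schedule as a symptom. That would raise the total in both arms and could shift the difference between them at that visit.

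**Working it through.** No stated figure in the plan bears on this point, so the check sets the sections side by side and adds a scale calculation.

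**1. What precedes each rating**

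| Rating | Preceding night |
|---|---|
| LHS+0 | Before wake therapy |
| LHS+1 | Wake-therapy night |
| LHS+2 | Recovery night (9.5.1), unless a failed wake night is repeated (10.3.3) |
| Post-intervention | About a week after the wake night |

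Only LHS+1 directly follows the imposed short night. LHS+2 is affected if the interview uses a longer recall frame or if the wake night was repeated.

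**2. What differs between arms.** LWT allows sleep from 21:00 to 01:00, which is 4 h. EWT allows 03:00 to 07:00, also 4 h. The difference in amount is 0 h. Hours slept cannot identify the arm; the part of the night spent awake can.

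**3. Reach of a disclosure.** There are four HRSD ratings in each treatment month, so eight in all. Each woman receives both treatments, so knowing the Month 3 arm fixes the Month 5 arm. A disclosure at LHS+1 of Month 3 comes before two further ratings that month and all four in Month 5. That is 6 of 8, including both post-intervention ratings.

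**4. Scale of a scoring shift at LHS+1.** Let b be the net between-arm shift in HRSD points from sleep items. The documents give no value; 0 to 2 points in either direction is an assumption. Inputs from Section 9.2 are N = 40, SD 9 (taken as the SD of the within-woman difference) and a planned difference of 3.15. For a two-sided paired test at .05, normal approximation, √40/9 = 0.703:

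- False-positive rate = Φ(0.703b − 1.96) + Φ(−0.703b − 1.96)
- Power if the true difference is 3.15 = Φ(0.703(3.15 ± b) − 1.96)

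| Size of b | Share of 3.15 | False positives | Power, shift against the effect | Power, shift with the effect |
|---|---|---|---|---|
| 0 | 0% | 5.0% | 60.0% | 60.0% |
| 0.5 | 16% | 6.4% | 46.1% | 72.7% |
| 1 | 32% | 10.8% | 32.7% | 83.1% |
| 2 | 63% | 29.0% | 12.5% | 95.1% |

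The paired t-test gives 10.5% and 27.8% for false positives at 1 and 2 points. It gives power of 57.9%, 31.4% and 12.4% for differences of 3.15, 2.15 and 1.15. These figures describe a test at one visit, which the plan does not specify. The 3.15 comes from earlier data on seven days of light alone, so it is a yardstick and not an expected day-1 effect. The 60.0% differs from the 71% stated in 9.2; that is a separate matter and nothing here depends on it.

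**5. Does the shift reach the main contrast?** A saturated treatment-by-time model gives each treatment its own mean at each time point. With complete data, a shift at LHS+1 leaves the post-intervention contrast unchanged; with missing data it can leak in only through the covariance. The individual slopes that 9.6 uses for the correlations could be affected if they include LHS+1 and LHS+2, which 9.6 does not settle.

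**The case against.** The outcome in 9.5.1 runs from Month 2 to post-intervention, and 6.2.4 gives the post-intervention label only to the LHS+8-9 rating. The saturated model keeps an LHS+1 artefact largely out of that contrast. This stands.

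A reader might infer that sleep items hide a rapid benefit of wake therapy, or make LWT look worse by up to 2 points. The documents do not support either. Acute effects already have their own measure: twice-daily visual analogue ratings of depressed mood, anxiety, lability and irritability from LHS+0 to LHS+2. Both arms are allowed 4 h of sleep, so much of any inflation may be common to both. Nor is the sign fixed: LWT imposes a 21:00 bedtime, while EWT ends sleep at 07:00 in women whose habitual wake time may be as late as 9 am (4.2), so either arm could score on early or late items. An experienced rater might also decline to score assigned wakefulness as insomnia.

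A reader might also infer that the rater certainly learns the arm. The documents show a likely route, not a certainty. An unblinded patient could let it slip in any call, and the BDI, as a self-rating, informs the rater only through how the forms are handled. Even so, LHS+1 is the call where the assignment is freshest and the questions most pointed, and no safeguard is written.

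**Conclusion.** The threat to the blind stands and is worth correcting. As written, the plan has the blind rater interview an unmasked patient the day after a sleep window whose timing identifies her arm. If disclosure occurs in Month 3, it precedes both post-intervention ratings. This rests on the assumption that the 24-item HRSD asks about early, middle and late insomnia. The size of any resulting rater bias cannot be derived from the documents.

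The scoring effect is secondary. LHS+1 totals may be raised in both arms, with a net difference of unknown size and sign; the figures above show sensitivity only. LHS+2 is affected only under a longer recall frame or after a repeated wake night. The plan's failure to say which ratings enter the main mood inference is what leaves this open.

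**What to change.** **Section 6.2.4.** Script the LHS+1 and LHS+2 HRSD calls so that the blind rater does not ask the sleep items. Tell women not to mention their sleep or light times to the rater. Have the research associate, who is already unblinded, handle the BDI forms from those two days, and reconcile 6.2 with 10.1 on who collects them. The monitoring of suicidal ideation during HRSD calls (7.1) is unchanged.

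**Section 9.6.** State that the primary mood contrast uses the post-intervention rating with full totals, and reconcile its timing (LHS+7/8 in Section 3, LHS+8-9 in 6.2.4). Analyse LHS+1 and LHS+2 HRSD and BDI only as totals without sleep items, against the same reduced totals at LHS+0. Do not drop sleep items at other visits: insomnia or hypersomnia is among the PMDD criteria listed in 4.3, and full totals are needed for eligibility, response and remission.

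**Cost.** A short call script, an instruction to patients and one paragraph of analysis text. Full HRSD totals will not exist at LHS+1 and LHS+2. The script must be in place before the calls, because rescoring cannot restore a blind already lost.

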Using a randomized cross-over design, in the luteal phase of their menstrual cycles, PMDD women will receive either 1) one night of LWT (sleep 21:00-01:00 h, followed by wakefulness) plus 7 days of AM BWL (light-emitting diode-LED administered for 60 minutes, starting within 30 minutes of habitual wake time) or 2) EWT (wakefulness until 03:00 h, then sleep 03:00-07:00 h) plus 7 nights of PM BWL (administered 90 minutes before habitual sleep onset, for 60 minutes). Following this first intervention, patients will undergo one washout month with no intervention. The second intervention will be completed in the luteal phase of the following month and will be the treatment opposite the one previously performed. Total study duration, including evaluations and washout, will be 5 months (see Figure 1, Section 3, for detailed study flow diagram).

Sample Size and Population

In order to achieve the targeted enrollment goal of 40 completed subjects allowing for a 20% drop-out rate, 48 PMDD women ages 18-45 will be recruited to participate in the study.

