2.2 Study Rationale

Interventions: The wake therapy and light interventions proposed in this application are based on our previous studies in PMDD³⁶⁻³⁹ and key published experiments by other investigators that indicate that the combined interventions are efficacious in other mood disorders after one week of treatment and maintained at 9-months follow-up.¹⁷⁻³¹ To provide optimal timing of interventions, we will administer wake therapy in the early-night vs. late-night and light pulses in the AM vs. PM at selected times in relation to sleep (within 30 min of waking and 90 min before sleep onset, respectively). These times were selected to examine phase-advance and phase-delay responses without disrupting sleep. Successful light treatment is associated with a phase-shift of the melatonin rhythm as noted by Epperson et al.⁴⁰ in a randomized trial of bright light therapy for antepartum depression and by Terman et al.⁴¹ in winter depression. In this proposal focusing on mood effects, we will administer 7 days of AM or PM light after wake and before sleep, respectively, for 60 min using a light-emitting diode (LED) device. The advantage of LEDs over conventional light boxes (fluorescent or incandescent) is that LEDs can be selected to emit light with energy concentrated at wavelengths of 450-480nm to which the human circadian system is most sensitive.⁴²⁻⁴⁴ Thus LEDs are not only more efficient, but smaller and light-weight, further enhancing patient compliance. Clinical effects on mood generally occur within 3-4 days after the onset of treatment, and expire within 3-4 days after discontinuation of treatment.^{45, 46}

A crossover treatment design will be employed to compare LWT+AM BWL vs. EWT+PM BWL responses within the same individual. As wake interventions lose effectiveness after 1 day, and light treatment effects after 3-4 days, we anticipate minimal carry-over effects of the wake plus light interventions administered a month

apart. To further ensure no carry-over effects, there will be a month of no-intervention between the 1st and 2nd treatments. Because our previous studies clearly indicated differences between PMDD and NC subjects occurred primarily in the luteal menstrual cycle phase, we will treat during this menstrual cycle phase rather than in the follicular phase.

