plastic screen)(The Litebook Company Ltd., Alberta Canada) with an intensity of 1,350 lux and an irradiance of 2.41×10^{-9} w/cm² at 20 in, and spectral emission peaks at 464 nm and 564 nm. Subjects will gaze at the light source for a minute every few minutes for 30 min. The distance of the subject from the light source will be calibrated individually for each light box by use of a Meterman LM631 Digital Light Meter (Meterman Test Tools, Everett, WA) to produce an intensity of 1,350 lux at 20.0 in. Ambient light intensity and spectra will be documented by the Actiwatch Spectrum. A research assistant will provide a measuring tape to ensure proper distance between light source and patient, check the Actiwatch recordings to ensure compliance, as well as the Litebook’s built-in compliance monitor recordings.

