Light Interventions: Subjects will sit in front of a portable (5.5" x 6.25") Litebook® Model 1.2 light box (an array of 60 cool white light-emitting diodes behind a clear plastic screen)(The Litebook Company Ltd., Alberta Canada) with an intensity of 1,350 lux and an irradiance of 2.41×10^{-9} w/cm² at 20 in, and spectral emission peaks at 464 nm and 564 nm. Subjects will gaze at the light source for a minute every few minutes for 60 min. The distance of the subject from the light source will be calibrated individually for each light box by use of a Meterman LM631 Digital Light Meter (Meterman Test Tools, Everett, WA) to produce an intensity of 1,350 lux at 20.0 in. Ambient light intensity and spectra will be documented by the Actiwatch Spectrum. A research assistant will provide a measuring tape to ensure proper distance between light source and patient, check the Actiwatch recordings to ensure compliance, as well as the Litebook's built-in compliance monitor recordings. Since most of us are exposed to fluorescent light in our everyday lives, we do not anticipate that exposure to bright light per se will pose any special physical, psychological, social or legal risks. The intensity planned is less intense than bright sunlight, which normally exceeds 10,000-50,000 lux. Although 1,350 lux is more intense than common indoor room lighting during a 16-hour day, the average patient would receive more radiation from room lighting than from 1-2 hours of special lighting. Thus, the treatment is expected to be less hazardous than going for a walk or going to the beach. No special side effects apart from mild sleepiness (the patient needs to be awake for the light exposure and evening light may potentially disrupt sleep onset) are anticipated. It should be noted that sleep deprivation has been reported to benefit depressed patients. The possibility that the bright light treatment might potentiate a depressed patient's risk of switching into mania is recognized, although we have not seen this effect in previous studies of PMDD patients and we will exclude bipolar patients with mania from the study. If hypomania occurs, the light would be discontinued and appropriate referral and treatment with psychotropic medication, if needed, would be given.

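### The light session is 30 minutes in one device paragraph of Section 3 but 60 minutes in seven other places; the text must be reconciled to one length

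*Combined protocol and SAP*

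**What the plan says.** The device is described twice, under Light Interventions in Section 3 and again under Light Interventions in Section 5.1. Both paragraphs give the same light box, intensity (1,350 lux at 20 inches), irradiance, spectral peaks, calibration procedure and compliance checks. They differ on how long the participant sits in front of it:

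- Section 3: "Subjects will gaze at the light source for a minute every few minutes for 30 min"
- Section 5.1: "Subjects will gaze at the light source for a minute every few minutes for 60 min"

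The Section 5.1 paragraph then goes on to safety text that Section 3 does not have, but none of that text concerns session length.

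Elsewhere the protocol gives the length as follows:

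- Précis, Interventions and Duration, morning light: "light-emitting diode-LED administered for 60 minutes, starting within 30 minutes of habitual wake time"; evening light: "administered 90 minutes before habitual sleep onset, for 60 minutes". The Randomization text of Section 6.2.2 and the treatment assignment text of Section 9.2 repeat both.
- Section 2.2: "we will administer 7 days of AM or PM light after wake and before sleep, respectively, for 60 min".
- Section 3, overall design: "We will randomize subjects to 60 min of either AM bright white light (LED of 1350 lux at 20 inches".
- Section 5.1, administration text: "subjects will receive, at home, 60 min of either AM bright white light (LED of 1350 lux at 20 inches".

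For the evening condition, Section 5.1 also fixes when the session stops: "PM bright white light ending 30 min before their habitual sleep onset time". The overall design text of Section 3 says the same.

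**The concern.** At a fixed intensity and distance, session length sets how much light each condition delivers. Two sentences that are otherwise the same give different lengths. Both are current instructions on using the device, not background or a description of earlier work. Section 3 also disagrees with itself, because its overall design text and its device paragraph give different figures.

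Treatment is self-administered at home, using materials and instructions that study staff prepare (Section 5.2). Staff then check delivery against the light box's built-in monitor and the Actiwatch recordings (Section 5.4). Both steps need a single session length to work from, and the protocol has no rule for which passage governs when two disagree.

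**Working it through.** **Step 1. Compare the two device sentences.** Word by word, the only difference is 30 against 60.

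**Step 2. Look for an explanation of 30 minutes.** It could be harmless if it meant only the gazing part of a longer session, or applied to one condition, one month or an earlier study. The Section 5.1 sentence describes the same intermittent gazing over 60 minutes, so the gazing-only reading fails. Neither paragraph limits itself to morning or evening light, to Month 3 or Month 5, or to previous work.

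**Step 3. List every stated session length.**

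| Place | Session length |
|---|---|
| Précis, Interventions and Duration | 60 min |
| Section 2.2 | 60 min |
| Section 3, overall design | 60 min |
| Section 3, Light Interventions | 30 min |
| Section 5.1, administration text | 60 min |
| Section 5.1, Light Interventions | 60 min |
| Section 6.2.2, Randomization | 60 min |
| Section 9.2, treatment assignment | 60 min |

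That is one place with 30 minutes and seven with 60.

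**Step 4. Check each length against the evening timing.** Read the 90 minutes in the Précis and Sections 6.2.2 and 9.2 as the start of the session. The end, in minutes before habitual sleep onset, is then 90 minus the session length:

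- 60-minute session: 90 − 60 = 30, which agrees with the end time in Sections 3 and 5.1.
- 30-minute session: 90 − 30 = 60, which does not agree.

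Working back from the stated end gives the same answer. A 30-minute session ending 30 minutes before sleep onset would start 30 + 30 = 60 minutes before it, not 90. Morning light has a start rule but no stated end, so no similar check is possible there.

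**Step 5. Size of the difference.** Inputs: 7 light days per treatment month and 1,350 lux in both device paragraphs.

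| | 30 min | 60 min |
|---|---|---|
| Minutes over 7 days | 7 × 30 = 210 | 7 × 60 = 420 |
| Nominal lux-hours per session | 1,350 × 0.5 = 675 | 1,350 × 1 = 1,350 |
| Nominal lux-hours over 7 days | 7 × 675 = 4,725 | 7 × 1,350 = 9,450 |

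The ratio is 2 on every line. The lux-hour figures are nominal, since participants look at the source only intermittently.

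The plan gives no total exposure to reproduce, and none of the calculations in Section 9.2 uses session length.

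**The case against.** The strongest reply is that this is an uncorrected copy of one paragraph. Sixty minutes appears seven times, including in the same section and in the section that governs administration, and the evening timing fits it. That is a fair account of the balance of the text, and it stands. A reader who saw only the two device paragraphs might infer two competing doses of equal standing, or an undecided dose. The documents do not support that reading. However, a count of passages is not a precedence rule, and the odd one out is in a paragraph that tells participants how to use the device.

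A reader might also infer that exposure would differ between women or between treatment months, and so bias the crossover comparison. That would depend on participant materials that are not in the documents. Section 5.2 has the study coordinator and research associate give the instructions, and nothing suggests they would use different lengths for different women or months. The 30-minute sentence does not separate morning from evening light. Followed uniformly, it would shorten both conditions alike and would not by itself create a difference in duration between treatments. The light box monitor and the Actiwatch could also reveal a departure.

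Finally, it is tempting to link this to the adherence threshold, since Section 5.4 counts days (at least 6 of 7) and does not say how many minutes make a completed day. That gap would remain if the 30-minute sentence were corrected. It is a separate matter and is not part of this point.

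**Conclusion.** The inconsistency is real, and no text in the documents explains it. One current instruction gives a session half as long as the one stated everywhere else: 210 against 420 minutes per treatment month at one intensity. The difference is in duration only. The conflict with the evening timing assumes that the 90-minute figure marks the start of the session; the direct contradiction between the two device sentences needs no assumption.

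The twofold figure measures the gap between the texts. It does not predict what participants would receive. Sample size, power and the endpoint definitions are unaffected. The correction matters because the parameter is part of the intervention itself. Which duration is right is for the sponsor to settle.

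**What to change.** Reconcile the Light Interventions paragraph of Section 3 with the Précis, Section 2.2, the overall design text of Section 3, both statements in Section 5.1, Section 6.2.2 and Section 9.2, so that the protocol states one session length. Check that the evening start and end times agree with the length chosen. Then confirm that the participant instructions and the compliance checks on the light box and Actiwatch recordings use the same figure. No new adherence rule is proposed.

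If only the outlying sentence has to change, the cost is a one-line protocol correction and a check of participant materials. There is no effect on sample size or on the planned analyses.
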